5.3 Baseline and reassessment CT scan

The baseline CT scan **must be within 4 weeks prior to the start of trial treatment**, so a repeat CT should be organised if required, remembering that randomisation cannot take place until *K-RAS* mutation status has been determined. Limited funding is available to contribute towards the cost of repeat baseline CT scans that are required only to meet the timelines set out in this protocol. Funding is available up to a limit of £150 per-patient at the time of writing this protocol. Please contact the CTRU for current funding availability.

Radiological reassessment is made **12 weeks after randomisation** ("12 week scan"), then at 12-weekly intervals, or sooner if clinically indicated, until disease progression ("follow-up scans"). It is recommended that the 12 week scan is pre-booked, at the time of starting treatment, **as near as possible to exactly 12 weeks after the date of randomisation** (with up to a further two weeks allowed in order to take account of practical issues).

If there is clinical evidence of disease progression at a time other than when radiological reassessment is due a CT scan should be carried out to confirm progression. A CT scan should always be carried out to confirm disease progression, unless there is a compelling reason not to.

Please note that copies of the baseline and the 12 week scan are required for external review. The preferred format is CD Rom, but hard-copy films are also acceptable. These should be forwarded to the PICCOLO team, CTRU, University of Leeds, [name] with their reports, as soon as possible after the 12 week scan has been performed. The scans and reports should be anonymised and labelled with the patient's trial number only. CTRU will provide pre-paid Special Delivery envelopes in which to send the CT scans for central review.

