11. STATISTICAL CONSIDERATIONS

11.1 Sample Size

Ir vs IrCs comparison

A non-inferiority design is proposed, based upon the proportion of patients progression-free at 12 weeks from randomisation. In a previous study in a similar patient population receiving irinotecan, median PFS was 4.2 months, with 63.3% of patients progression-free at 12 weeks.³⁸ There are no previous best supportive care (BSC) trials that have included regular CT scan assessments, however in a trial comparing irinotecan with BSC, at the time point that 63% of Ir

patients were alive, less than 40% of BSC patients were alive⁴⁰. On this basis we have estimated that a similar proportion – 40% - of patients on BSC would be expected to be progression-free at 12 weeks applying standard WHO or RECIST criteria. On this basis irinotecan contributes at least 23% to the proportion of patients progression-free at 12 weeks. On the basis of clinician consensus IrCs will be defined as no worse than Ir if median PFS is at least 3 months with IrCs, equivalent to at least 52.7% of patients in the IrCs arm progression-free at 12 weeks. This corresponds to a reduction of no more than 10.6% in the proportion of patients progression-free at 12 weeks which is our non-inferiority margin; retaining more than half the effect that irinotecan has over BSC. The sample size calculation for the Ir vs. IrCs comparison remains the same since there is no data to suggest that *K-RAS* status is a predictive factor for Irinotecan or Ciclosporin.

We will conduct a one-sided test for non-inferiority.³⁹ With 80% power and a significance level of 2.5%, 680 patients are required to test for this degree of non-inferiority using a one-sided chi-squared test without continuity correction. To account for a 10% drop-out or 5% cross-over, 750 patients (375 per arm) would need to be randomised in total. This sample size also gives over 90% power for claiming non-inferiority of PFS using a one-sided modified log-rank test with significance level 2.5% (at least 273 PFS events are required to assess non-inferiority with 80% power), and allows detection of a clinically relevant relative reduction of 50% (from 20% with Ir to 10% with IrCs) in the proportion of patients experiencing grade 3+ diarrhoea within 12 weeks of randomisation, with over 90% power and at a 5% (two-sided) significance level, using a two-sided chi-squared test without continuity correction.

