Analysis of 12-week assessments will include all patients assessed between 10 and 14 weeks from randomisation. A sensitivity analysis will be conducted to allow for patients assessed outside of this 2 week time frame. Analysis of response will be performed using the centrally reviewed outcome. If the centrally reviewed outcome is missing, the primary analysis will class the patient as being progression-free at 12 weeks (if alive), and a sensitivity analysis will be conducted using the outcome of the local assessment. If this is also missing, the patient will be classed as having progressed at 12 weeks in the sensitivity analysis.

A two-sided 5% significance level will be used for all superiority endpoints, and a one-sided 2.5% significance level will be used for all non-inferiority endpoints.

Safety data (adverse events and serious adverse events as detailed in Section 8) will be presented for all patients by treatment group and comparison, and by relationship to study drug, or underlying colorectal cancer.

Ir vs IrCs comparison

All patients randomised to receive either Ir or IrCs via protocol Version 1.0 or to the Ir vs. IrCs comparison under protocol Version 2.0 (i.e. mutant/unknown *K-RAS* status), regardless of previous anti-EGFR targeted therapy use, will be included in this comparison.

Primary Endpoint

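### The primary analysis scores a living patient with no central 12-week read as progression-free, even where progression is documented locally

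*Protocol*

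**What the plan says.** The opening part of Protocol Section 12 bases the 12-week outcome on central review. For a patient without one it says: "If the centrally reviewed outcome is missing, the primary analysis will class the patient as being progression-free at 12 weeks (if alive"). The local outcome is used in a sensitivity analysis. A patient is scored as progressed only in that sensitivity analysis, and only if the local outcome is missing too. The Ir versus IrCs primary endpoint paragraph of Section 12 keeps the same order, and nothing elsewhere in the protocol reverses it.

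On scans, Section 5.3 says "Please note that copies of the baseline and the 12 week scan are required for external review". Section 9 specifies external confirmation for baseline and 12-week scans, but also says that baseline and subsequent scans are forwarded for external review.

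The margin is in Section 11.1: "median PFS was 4.2 months, with 63.3% of patients progression-free at 12 weeks" on Ir, "equivalent to at least 52.7% of patients in the IrCs arm progression-free at 12 weeks", and so "a reduction of no more than 10.6% in the proportion of patients progression-free at 12 weeks which is our non-inferiority margin".

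**The concern.** Section 2 defines the Ir versus IrCs primary outcome as being alive and showing no evidence of progression at 12 weeks. A patient with progression on the local scan, or recorded clinically, has such evidence. Section 12 nevertheless scores that patient as a success whenever the central read is absent.

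In a non-inferiority comparison this is usually the unsafe direction. Giving the same favourable value to missing patients in both arms pulls the two observed proportions together, so an IrCs arm that is truly at the margin looks closer to control. Elsewhere Section 12 is careful about this. It counts non-cancer deaths within 12 weeks as progression in the main analysis, and it gives the per-protocol analysis equal weight because intention-to-treat is less conservative here. The missing-read rule works the other way, and the per-protocol analysis is not exempted from it.

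Missing reads may also be related to outcome. A patient who progresses early may not attend for the 12-week scan, and the protocol does not say that an earlier scan showing progression supplies the 12-week central outcome.

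**Working it through.** **Inputs (Section 11.1).** Ir 63.3%; IrCs at the margin 52.7%; margin 10.6 points; one-sided 2.5%; 375 per arm.

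**The plan's own figure.** "With 80% power and a significance level of 2.5%, 680 patients are required to test for this degree of non-inferiority". With the pooled two-proportion formula and no continuity correction, mean proportion 0.580:

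n per arm = [1.960·√(2·0.580·0.420) + 0.842·√(0.633·0.367 + 0.527·0.473)]² / 0.106² = 339.2, so 340 per arm and 680 in total. This matches. For drop-out, 680/0.90 = 756 and 680 × 1.10 = 748, both close to the stated 750.

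**Effect of the rule.** Let m be the share with no central read, equal in both arms and unrelated to outcome. The observed proportion is p′ = m + (1 − m)p, so a true deficit of 10.6 points becomes (1 − m) × 10.6. Since m + (1 − m)p = p + m(1 − p), the same figures apply if only progressors lack a read and m is the share of them affected.

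Type I error on the difference scale = Φ[(0.106 − observed deficit)/SE − 1.96], with SE = √[(p′₁(1 − p′₁) + p′₂(1 − p′₂))/375].

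Section 12 also names the odds ratio as the basis of the primary analysis. The margin as an odds ratio is (0.527/0.473)/(0.633/0.367) = 0.646. Type I error on that scale = Φ[ln(observed OR/0.646)/SE − 1.96], with SE the usual log-odds-ratio standard error.

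Example, m = 10%:
- The observed rates are 66.97% and 57.43%, a deficit of 9.54 points with SE 3.52 points. Φ(1.06/3.52 − 1.96) = 4.9%.
- The observed odds ratio is 0.665 with SE 0.152 on the log scale, which gives 3.9%.

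| m (assumed) | Observed deficit (points) | Type I error, difference | Type I error, odds ratio |
|---|---|---|---|
| 0% | 10.6 | 2.5% | 2.5% |
| 5% | 10.1 | 3.5% | 3.2% |
| 10% | 9.5 | 4.9% | 3.9% |
| 15% | 9.0 | 6.6% | 4.6% |
| 20% | 8.5 | 9.0% | 5.4% |

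Simulation of 400,000 trials per row agreed on the difference scale (3.5%, 4.8%, 6.6%, 9.0%). The formula ignores the condition that the patient be alive. Deaths are not recoded, so m is strictly the share of failures recoded, and the effect is somewhat smaller if deaths fall in proportion to failures.

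**Unequal missingness, difference scale.**
- 5% on Ir and 10% on IrCs: observed 65.1% and 57.4%, deficit 7.7 points, type I error 12.6%.
- 10% on Ir and 5% on IrCs: observed 67.0% and 55.1%, deficit 11.9 points, type I error 1.0%.

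**Alternatives.**
- Local read used where the central read is missing, assuming the two agree: the 10.6-point deficit is kept and type I error is 2.5%. Power at equal rates is 85% with 375 per arm.
- All missing scored as progressed, m = 10%: observed 57.0% and 47.4%, deficit again 9.5 points. Type I error is 4.8% on the difference scale and 5.5% on the odds-ratio scale.

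**The case against.** Several parts of the opposing case stand.

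- A reader might infer from Section 5.3 that scanning stops at progression, so that every early progressor is scored a success by design. The text does not support that. The phrase "then at 12-weekly intervals, or sooner if clinically indicated, until disease progression" governs the later follow-up scans. Section 7.6 orders the 12-week CT without condition, Section 10.4 calls that time point mandatory, and only Section 7.7 limits scans to patients who have not yet progressed. Early progressors may still miss the scan in practice, but the protocol does not plan it.
- A reader might take the drop-out figure in "To account for a 10% drop-out or 5% cross-over, 750 patients (375 per arm) would need to be randomised in total" as the missing-read rate. It is only a sample-size allowance.
- The bias does not always favour IrCs. It reverses if clearly more reads are missing on Ir.
- The reach of the rule is uncertain. The same paragraph of Section 12 opens by including patients assessed between 10 and 14 weeks, so the rule may cover only patients assessed in that window. The text does not say whether an unassessed patient is excluded or imputed.
- The planned sensitivity analyses would show a fragile result, and in an open-label trial there is a respectable motive for keeping unblinded local reads out of the primary outcome.

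None of this changes the primary rule. If the primary and sensitivity analyses disagree, the conclusion rests on the one that disregards documented progression.

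**Conclusion.** The rule is wrong as written: it contradicts the endpoint in Section 2 and, under the likelier patterns of missingness, makes a false claim of non-inferiority easier. Its size depends on a missing-read rate that the protocol does not give. At an assumed 10% missing, equal and at random, one-sided type I error is about 4.9% on the difference scale and 3.9% on the odds-ratio scale, against 2.5%. Across 5% to 20% the ranges are 3.5% to 9.0% and 3.2% to 5.4%. With nearly complete central reads the effect is negligible. These figures assume true rates exactly at the margin, 375 per arm, and unadjusted normal approximations. The protocol supports neither a claim that the bias is certain in direction nor one that it is large.

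**What to change.** 1. In the primary analysis, when the central read is missing, use the local RECIST or clinical outcome, so that any documented progression or death by the 12-week assessment is a failure. Move the present rule to a sensitivity analysis.
2. For patients with neither read, do not rely on one fixed value for both arms, since scoring them all as failures also dilutes the difference. Use multiple imputation or an arm-specific tipping-point analysis.
3. Reconcile the rule with the 10-to-14-week inclusion sentence in Section 12, saying who is imputed and who is excluded.
4. State in Sections 5.3 and 9 whether an earlier scan showing progression supplies the 12-week central outcome.

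The cost is wording: Section 7.6 already collects the RECIST response and clinical evidence of progression. The downside is small. Unblinded local reads would decide the outcome for the patients without a central read, and observed progression-free proportions would be a little lower.

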2. AIMS AND OBJECTIVES

PICCOLO has two separate clinical objectives. These are:

Objective 1 (irinotecan modulation with ciclosporin): to establish whether the toxicity of irinotecan therapy is reduced, without loss of efficacy, by modulation with ciclosporin

Objective 2 (addition of panitumumab): to establish whether, in patients with *K-RAS* wild-type tumours, the efficacy of irinotecan therapy is improved by the addition of panitumumab

To address these objectives, the trial poses specific questions using primary and secondary endpoints, fully described in section 10. The general approach is:

Objective 1 (comparison: Ir versus IrCs).

- A sensitive primary outcome measure – proportion of patients alive without evidence of disease progression 12 weeks after randomisation – is used to establish non-inferior anti-cancer efficacy for the **IrCs** combination
- Provided this non-inferiority condition is satisfied, secondary outcome measures will be used to determine whether **IrCs** has improved tolerability (reduced diarrhoea; reduced overall toxicity; improved patient acceptability and/or improved quality of life). In addition, overall survival will be used as a secondary outcome measure to confirm non-inferiority.

Objective 2 (comparison: Ir versus IrPan).

- A robust primary outcome measure – overall survival – is used to establish whether, in patients with *K-RAS* wild-type tumours not previously treated with anti-EGFr therapy, **IrPan** has superior efficacy to Ir.
- Secondary outcome measures will be used to compare the toxicity, patient acceptability and quality of life associated with the two regimens in patients not previously treated with anti-EGFr therapy. Secondary anti-cancer efficacy measures of disease response and progression will also be applied to assess superiority of IrPan in these patients.
- A small proportion of patients will have received a prior anti-EGFR targeted therapy. They will be considered in a separate exploratory comparison of efficacy using a sensitive outcome measure (proportion of patients progression-free at 12 weeks) to address the question whether panitumumab enhances irinotecan sensitivity in this context and to also assess toxicity. This exploratory analysis will consider only those patients with wild-type *K-RAS* status who have previously received an anti-EGFR targeted therapy.

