Analysis will be based on the lower limit of the 95% confidence interval (CI) (one-sided type I error rate of 2.5%) of the difference in proportion of patients progression free at 12 weeks from randomisation between each treatment group. Logistic regression will also be used to adjust for the minimisation factors, previous anti-EGFR targeted therapy use and any other covariates identified to influence patients' prognosis. Treatment and covariate estimates with corresponding 95% CIs will be given. To account for any deaths from causes other than colorectal cancer which may occur within 12 weeks of randomisation, for whom no evidence of disease progression was found, sensitivity analyses will be conducted classifying these patients as progression-free (these patients will be classed as having progressive disease at 12 weeks in the main analysis). Sensitivity analysis will also be conducted to account for patients with missing data regarding progression at 12 weeks, using the local assessment or classifying these patients as with progressive disease, as appropriate. The primary analysis will be based on the lower limit of the confidence interval of the odds ratio for the proportion of patients progression free at 12 weeks, obtained using logistic regression which adjusts for the minimisation factors.

Secondary Endpoints

The difference in proportion of patients who are free from treatment failure, defined as clinical or radiological progression, death due to colorectal cancer or toxicity, or termination of treatment irrevocably, at 12 weeks from randomisation between treatment groups will be compared using a two-sided chi-squared test. Logistic regression will also be used to adjust for the minimisation factors, previous anti-EGFR targeted therapy use and any other covariates identified to influence patients' prognosis. Treatment and covariate estimates with corresponding 95% CIs will be given. Sensitivity analyses will be conducted to allow for any deaths from causes other than colorectal cancer within 12 weeks of randomisation. Sensitivity analysis will also be conducted to account for patients with missing data regarding treatment failure at 12 weeks, classifying these patients as with treatment failure.

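### The sensitivity analysis of 12-week progression-free status makes no exception for treatment-related deaths, so a toxic death without documented progression counts as a success

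*Protocol*

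**What the plan says.** Protocol section 12, Ir vs IrCs, Primary Endpoint, sets the main-analysis rule: "these patients will be classed as having progressive disease at 12 weeks in the main analysis". The patients meant are those with "deaths from causes other than colorectal cancer which may occur within 12 weeks of randomisation", provided that they are also patients "for whom no evidence of disease progression was found". The alternative scoring of this group is then given: "sensitivity analyses will be conducted classifying these patients as progression-free". Two conditions thus select the deaths to be rescored: the cause is not colorectal cancer, and no progression was found. Relation to trial treatment is not mentioned.

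Section 12, Ir vs IrPan, Secondary Endpoints, repeats the rule for the 12-week proportion in that comparison, with the same two conditions and the same scoring.

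Three other places bear on it:

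- Section 2, Objective 1, describes the outcome as the "proportion of patients alive without evidence of disease progression 12 weeks after randomisation".
- Section 12, Ir vs IrCs, Secondary Endpoints, defines treatment failure at 12 weeks to include "death due to colorectal cancer or toxicity", so toxicity is named there as a cause of death distinct from the cancer.
- Section 7.9 has date and cause of death recorded for every death.

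**The concern.** A death from toxicity is, in the protocol's own terms, not a death from colorectal cancer. The first mandatory scan is at 12 weeks (sections 5.3 and 10.4), so a patient who dies of toxicity earlier will often have no documented progression. Such a patient meets both conditions and moves from failure to success.

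Toxic death is foreseeable here. Section 1 describes irinotecan diarrhoea with myelosuppression as potentially life-threatening, and says that panitumumab had not previously been combined with single-agent irinotecan.

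A sensitivity analysis shows readers whether the main result is robust. This one credits an arm for deaths that its treatment caused. It could make a toxic arm look closer to, or further ahead of, its comparator, and it could make a safer arm look less robust than it is.

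**Working it through.** **Inputs.** From section 11.1: 63.3% progression-free at 12 weeks on Ir, 52.7% as the lowest acceptable value on IrCs, a margin of 10.6 points, one-sided 2.5% significance, 80% power, 680 patients needed and 750 randomised (375 per arm). From section 3: 240 per arm for Ir vs IrPan. The documents give no rate of toxic death, so every such rate below is an assumption.

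**The plan's own figure.** For a chi-squared test without continuity correction, with mean proportion 0.58:

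n per arm = [1.960·√(2·0.58·0.42) + 0.842·√(0.633·0.367 + 0.527·0.473)]² / 0.106² = (1.368 + 0.584)² / 0.01124 ≈ 339.2, rounded up to 340.

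That is 680 in total, as stated. Nothing here disputes the sample size.

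**Effect of one rescored death.** 1/375 = 0.27 points in an Ir or IrCs arm; 1/240 = 0.42 points in an arm of Ir vs IrPan. A one-point excess in an arm of 375 is about 4 deaths (0.01 × 375 = 3.75).

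**Effect on the confidence limit.** The lower 95% limit of the difference (IrCs minus Ir) is d − 1.96·√[p₁(1−p₁)/375 + p₂(1−p₂)/375]. The difference scale is used because the margin is stated on it. Assume main-analysis proportions of 63.3% (Ir) and 59.3% (IrCs):

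−0.040 − 1.96·√[(0.2323 + 0.2414)/375] = −0.040 − 0.0697, or −10.97 points.

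This just misses the margin. The 4-point deficit was chosen to lie near the boundary: with 375 per arm, an observed deficit of about 3.6 points is the most that passes. Now add the rescored deaths to each arm's successes:

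| Toxic deaths without progression, Ir / IrCs (assumed) | Difference | Lower limit |
|---|---|---|
| none (main analysis) | −4.0 | −10.97 |
| 1% / 1% | −4.0 | −10.93 |
| 1% / 2% | −3.0 | −9.91 |
| 1% / 3% | −2.0 | −8.90 |
| 3% / 1% | −6.0 | −12.89 |

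At equal rates almost nothing changes. A one-point excess on IrCs turns a miss into a pass in this check.

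**The mirror case.** Assume 63.3% and 60.3% in the main analysis, and toxic deaths of 2% on Ir and 1% on IrCs.

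- Main: −0.030 − 1.96·√[(0.2323 + 0.2394)/375] = −9.95 points, a pass.
- Sensitivity, at 65.3% and 61.3%: −0.040 − 1.96·√[(0.2266 + 0.2372)/375] = −10.89 points, a miss.

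Here IrCs, the safer arm, appears to lose robustness because fewer of its patients died of toxicity. In every scenario the main-analysis result is unchanged.

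**The case against.** The strongest reply is that the main analysis already counts all these deaths as failures, and that is where non-inferiority is decided. This stands, and it sets the severity. It is also fair that a sensitivity analysis departs from the main rule on purpose, so differing from section 2 is not in itself an error. That does not justify this particular departure: rescoring a death unrelated to disease and treatment asks a sensible question about competing causes, whereas rescoring a treatment-related death counts harm as efficacy.

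The text never mentions toxic deaths, so their inclusion follows from a missing exception. The authors may have meant unrelated deaths only, and a SAP could say so. But the rule as fixed in the Protocol includes them, and the treatment-failure definition shows that toxicity was regarded as a separate cause.

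Toxic deaths are visible elsewhere: in overall and progression-free survival (death from any cause), in treatment failure for Ir vs IrCs, in 60-day all-cause mortality by arm, and in the reporting of all deaths to the DMEC (section 8.4). They would not go unseen.

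A reader might infer three stronger things that the documents do not support:

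- **That the trial's false-positive rate for non-inferiority is inflated.** With the true difference at the margin and 375 per arm, the chance that this check meets the margin rises from 2.5% to 4.7%, 8.1% or 13% under assumed toxic-death rates (Ir vs IrCs) of 1% vs 2%, 1% vs 3% or 2% vs 5%. But section 12 attaches no decision rule to this analysis, so these are not error rates of the trial. They also assume an excess on IrCs, whereas the rationale in section 1 is that ciclosporin reduces irinotecan's main toxicity.
- **That every non-cancer death is rescored.** Only those without evidence of progression are.
- **That panitumumab could be declared beneficial because it killed patients.** The primary endpoint there is overall survival, with death from any cause; the 12-week proportion is secondary.

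**Conclusion.** The point holds as a minor defect in one sensitivity analysis, stated in two places. Read literally, treatment-related deaths within 12 weeks without documented progression are rescored as successes, so the check leans towards whichever arm has more of them. Each such death is worth 0.27 points in an arm of 375, and a one-point excess shifts the difference by one point in either direction. That is about 9% of the margin (1/10.6), enough to change how the check reads only when the result lies close to the margin. The size rests on assumed toxic-death rates; the direction depends on which arm has the excess and is unknown in advance. The primary conclusion of neither comparison is affected.

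**What to change.** In section 12, in the Primary Endpoint paragraph for Ir vs IrCs and the Secondary Endpoints paragraph for Ir vs IrPan, limit the rescoring to deaths without evidence of progression that are recorded as due neither to colorectal cancer nor to trial treatment. State that treatment-related deaths remain failures in every analysis.

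This takes one sentence in each of two places. Cause of death is already collected, and sample size, main analysis and trial conduct do not change. The cost is that the sensitivity analysis covers fewer deaths. It also still depends on cause of death as attributed in an open-label trial: separating toxic from unrelated deaths is itself a judgement by people who know the allocation, and this change does not cure that.

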10.4 Choice of Primary Endpoint

Ir vs IrCs comparison

A non-inferiority trial requires a sensitive discriminator of efficacy. To use PFS for this purpose would require CT scanning at a frequency close to the difference being excluded, which in this trial is less than 6 weeks. Response rate is insensitive given the low rate of objective responses (<10%) with the standard therapy. OS is subject to influence by subsequent treatment. In contrast the proportion of patients free of progression at 12 weeks can be determined reliably with a single mandatory scan/assessment point, and the expected progression-free proportion of approximately 65% with standard therapy is a good basis for comparison.

Ir vs IrPan comparison (patients with wild-type K-RAS status not previously receiving an anti-EGFR targeted therapy)

The choice of OS for the primary endpoint for the +/- panitumumab comparison reflects the fact that for a novel therapy to be adopted into standard care, given known skin toxicity and likely cost, it would require a significant tangible benefit, and OS is objective and well accepted. Worthwhile treatment given at a relatively late stage in the disease should produce an OS effect. Furthermore this endpoint is reliable and avoids the need for very frequent scanning which is both arduous for patients and expensive. Hence our primary endpoint for the +/- panitumumab comparison is OS. The use of three secondary efficacy endpoints (PFS; RR; Progression-free at 12 weeks) ensures that a lesser efficacy benefit, requiring further phase III trials, would not go un-noticed.

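### Ir vs IrCs: the analysis named primary is an adjusted odds ratio, but the only non-inferiority margin is an absolute 10.6 points, and the same paragraph also bases the conclusion on the difference in proportions

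*Protocol*

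**What the plan says.** Section 11.1 (Sample Size, Ir vs IrCs) sets the margin. The reference study gave "median PFS was 4.2 months, with 63.3% of patients progression-free at 12 weeks". The lowest acceptable result for IrCs is a median PFS of 3 months, "equivalent to at least 52.7% of patients in the IrCs arm progression-free at 12 weeks". The text then defines "a reduction of no more than 10.6% in the proportion of patients progression-free at 12 weeks which is our non-inferiority margin". The size is set on the same scale: "With 80% power and a significance level of 2.5%, 680 patients are required to test for this degree of non-inferiority". The calculation compares the two proportions directly, "using a one-sided chi-squared test without continuity correction". This is raised to 750 randomised (375 per arm) for drop-out or cross-over.

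Section 12 (Ir vs IrCs, Primary Endpoint) begins "Analysis will be based on the lower limit of the 95% confidence interval (CI") of the difference in the proportion progression-free at 12 weeks, and adds that logistic regression will also be used. The last sentence of the same paragraph reads "The primary analysis will be based on the lower limit of the confidence interval of the odds ratio" for that proportion, from logistic regression adjusted for the minimisation factors.

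The protocol states no odds-ratio margin and no rule for converting the 10.6 points to an odds ratio. Section 10.4 gives a slightly different planning rate: "the expected progression-free proportion of approximately 65% with standard therapy is a good basis for comparison".

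**The concern.** A superiority analysis can move from a difference to an odds ratio without a new threshold, because the null value (0 or 1) follows from the scale. A non-inferiority analysis cannot, because the lower limit must be compared with a margin on its own scale. Here the analysis labelled primary yields a lower limit for an odds ratio, and the protocol has nothing to compare it with. The analysis that does have a threshold, the difference in proportions, is introduced first as the basis of the analysis and then displaced.

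Two further points follow. A fixed odds ratio corresponds to a different absolute loss at each control rate, so the scales agree only close to the planned rate. And the odds ratio from a logistic model is conditional on the covariates, so it is not the same quantity as the marginal odds ratio implied by two planning percentages.

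This decision gates Objective 1. Section 2 uses the tolerability outcomes to judge IrCs provided non-inferiority is met, and the pooled subgroup analyses in section 12 depend on it too.

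**Working it through.** **Inputs.** Control rate 63.3%, lowest acceptable IrCs rate 52.7%, margin 10.6 points, one-sided 2.5%, 80% power, 680 evaluable, 750 randomised (all section 11.1). Control rate of about 65% (section 10.4).

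**1. Reproduce the stated size.** One-sided chi-squared test, pooled variance under the null, no continuity correction, mean rate (0.633 + 0.527)/2 = 0.580:

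n per arm = [1.960 × √(2 × 0.580 × 0.420) + 0.842 × √(0.633 × 0.367 + 0.527 × 0.473)]² / 0.106² = 339.2, rounded up to 340, so 680 in total.

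This matches exactly, so the trial was sized on the absolute difference.

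**2. Odds ratio implied by the planning rates.** (0.527/0.473) / (0.633/0.367) = 1.114/1.725 = 0.646, log −0.437. The protocol does not state this value.

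**3. What a fixed 0.646 allows at other control rates.** For control rate p, IrCs odds = 0.646 × p/(1 − p), converted back to a proportion:

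| Control rate | Loss allowed by OR 0.646 | OR equal to a 10.6-point loss |
|---|---|---|
| 50% | 10.8 points | 0.650 |
| 55% | 10.9 | 0.653 |
| 63.3% | 10.6 | 0.646 |
| 65% | 10.5 | 0.642 |
| 70% | 9.9 | 0.627 |
| 75% | 9.0 | 0.603 |
| 80% | 7.9 | 0.567 |

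**4. Can the rules disagree?** 375 per arm, unadjusted Wald 95% limits, pass if above −10.6 points or above 0.646:

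| Progression-free, Ir vs IrCs | Lower limit, difference | Lower limit, OR |
|---|---|---|
| 237 vs 224 (63.2% vs 59.7%) | −10.4 points, passes | 0.643, fails |
| 281 vs 266 (74.9% vs 70.9%) | −10.4 points, passes | 0.591, fails |
| 188 vs 175 (50.1% vs 46.7%) | −10.62 points, fails | 0.653, passes |

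With the Ir count held fixed, the number of IrCs counts giving opposite verdicts is 1 at a 63.3% control rate, 4 at 70%, 7 at 75% and 12 at 80%.

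**5. Power on each scale, true rate 63.3% in both arms.**

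- Difference, 340 per arm: Φ(0.106/√(2 × 0.633 × 0.367/340) − 1.96) = Φ(0.907) = 81.8%.
- Odds ratio, 340 per arm: Φ(0.437/√(2/(340 × 0.633 × 0.367)) − 1.96) = Φ(0.786) = 78.4%.
- Odds ratio, 375 per arm: Φ(0.924) = 82.2%. The difference scale gives 85.3%.
- With 75% in both arms and 375 per arm: 91.8% (difference) and 73.6% (odds ratio).

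**6. Conditional versus marginal odds ratio.** The documents do not give the prognostic strength of the covariates. If the linear predictor has a standard deviation of 0.5 to 1.0 on the logit scale (assumption), marginal rates of 63.3% and 52.7% correspond to a conditional odds ratio of about 0.63 to 0.59, not 0.646.

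**The case against.** The strongest reply is that the protocol does name one primary analysis. The Ir vs IrPan text in section 12 has the same structure: an unadjusted comparison, an adjusted model, then a closing statement that the adjusted model is primary. Read that way, the difference in proportions is the unadjusted companion, and the opening sentence is loosely worded. This largely stands: the label is clear. It does not supply the threshold, which Ir vs IrPan does not need because it is a superiority test.

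A reader might infer that the rule cannot be applied at all. The documents do not support that. Both boundary rates are printed, and 0.646 follows from them in one line. The rule is incomplete as written but can be repaired.

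A reader might also infer that the margin or scale would be chosen after seeing the data. That is not shown. Section 12 says an analysis plan for Protocol Version 1.0 was finalised, that changes to it will be documented, and that those who agreed it stay blinded. That plan is not available here and may state an odds-ratio margin. It would still leave the two bases in the protocol's own paragraph and the mismatch with section 11.1.

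The practical effect near the design rate is small. At 65% the two margins differ by about 0.1 point. Between 45% and 65% the fixed odds ratio is never more than about 0.3 points looser. At higher control rates, and when 0.646 is applied to a conditional odds ratio, the odds-ratio rule is the stricter one, so the risk there is lost power rather than an easier false claim. All of this stands.

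Control rates above plan are nevertheless plausible. Section 12 classes living patients with missing central review as progression-free in the primary analysis. If 10% to 20% were missing (assumption), 63.3% could rise to at most 63.3 + 0.10 × 36.7 = 67.0% or 63.3 + 0.20 × 36.7 = 70.6%.

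**Conclusion.** The point holds as a defect in the decision rule. The protocol gives two bases for one non-inferiority conclusion, and the one it labels primary has no margin on its own scale. If 0.646 is taken as the implied margin, the two rules disagree in a one-patient band at the planned 63.3% and over 7 to 12 patients at 75% to 80%.

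The sample size is not wrong. The figure of 680 reproduces, and power on the odds-ratio scale is 78.4% with 680 evaluable and 82.2% if all 750 are evaluable, against the 80% planned. It would be a mistake to read this point as a claim that the trial is materially underpowered.

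These figures rest on unadjusted Wald intervals and on equal true rates in the two arms for power. The conditional odds-ratio range rests on an assumed covariate strength and shows direction only.

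**What to change.** State one rule in section 12: non-inferiority is concluded if the lower 95% limit of the risk difference (IrCs minus Ir) is above −10.6 percentage points, with the difference standardised from the logistic model containing the minimisation factors. Report the adjusted odds ratio as supportive. This keeps the covariate adjustment, and the margin and sample size in section 11.1 stay as they are.

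An odds-ratio primary is also legitimate if completed. In that case:

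- state its margin in advance (0.646 at the planning rates), noting that this is a marginal value applied to a conditional estimate;
- reword the opening sentence of the paragraph so that the difference in proportions is clearly supportive;
- give power on that scale, about 78% at 680 evaluable and about 82% at 750.

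Either route costs one paragraph in the protocol, with the analysis plan brought into line. The first adds a standard post-estimation step. Neither needs extra patients or data.
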